#### **Statistical analysis method**

- PLT and other mean variation trends were processed by repeated measurement data analysis of variance; Kaplan-Meier survival analysis was used to estimate the recovery of PLT count, cumulative predicted survival rate, cumulative recurrence rate of malignant hematologic disease, cumulative mortality associated with transplantation, and cumulative incidence of GVHD, and log-rank test was performed. Independent sample nonparametric test was used to analyze the accumulative demand of PLT suspension. The statistical process and graph were all run on SPSS 13.0 software. All tests were bilateral, and  $P \leq 0.05$  was considered to be significant. The PLT recovery time, granulocyte implantation time and PLT infusion number were compared by one-way analysis of variance. OS and DFS are estimated by Kaplan-Meier method. Risk factor analysis: variables: age, sex, HLA match, CD34+ cell number, incidence of GVHD within 100 days after transplantation, CMV infection rate. Multivariate Cox regression analysis was performed on the factors with significant differences ( $P < 0.05$ ) by one-way analysis of variance.

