**Withdrawal criteria**

1. PLT remains less than  $20 \times 10^9/L$  after two weeks' treatment of avatrombopag in a maximum dose of 60

	
mg/d (Solution: receive other treatment after withdrawal from the study);
 
 
2. The participant or his legal guardian requests a withdrawal ;
 
3. c poor compliance(medicine taken less than 80% of the prescribed amount or more than 120% of the prescribed amount);
 
4. With requirement of a medicine that is prohibited in the study;
 
5. With adverse events that discontinues the study;
 
6. With some unexplained serious complications;
 
7. Be pregnant during treatment;
 
8. Deemed unsuitable for further study by the investigator.
 
 
Trial Termination
 
 
1. Sponsor decides to stop the trial for safety reasons;
 
2. Independent ethics committee decides to stop the trial;
 
3. Principal investigator decides to stop the trial.
 

Investigational Product
	
 
• Name: avatrombopag;
 
• Dosage form: tablet;
 
• Specification: 20 mg/tablet.
 

Treatment Design
	
 
• The whole study is divided into two stages, including 4-weeks' core study and 4-weeks' extended study;
 
• During the core study, participants are randomly assigned into the avatrombopag group and the rhTPO treatment group(standard group) with 1:1 ratio. The initial dose of avatrombopag is 20 mg/d. If the patient's PLT count remains less than <math>20 \times 10^9/L</math> after one week, the maximum dose was increased to 40 mg/d.
 
 
Avatrombopag will be taken orally with food. The rhTPO

will be subcutaneously injected with dosage of 300 U/kg/d;

- After the end of the core study, participants in the avatrombopag group who does not meet the withdrawal indication can be enrolled in the extended study and continue the avatrombopag treatment with a maximum dose of 60 mg/d. Participants who does not respond to treatment in the rhTPO group (PLT < 20\*10^9/L ) can also be enrolled in the extended study to receive avatrombopag treatment, by titrating avatrombopag in the dose of 20-60 mg/d according to the participants' condition;

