- Patients who achieved PLT reconstruction during the core study and the extended study period are followed up to 4 weeks after investigational product withdrawal, and PLT count is measured for one time during the follow up;
- Adjustment Indication: When PLT ≥ 50\*10^9/L excluding the factor of blood transfusion, the dosage of avatrombopag and rhTPO will be eventually decreased and stopped according to clinicians.

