
process
	
 
1. Informed consent;
 
2. Subject's demographic information and basic information;
 
3. Medical history, current treatment, concomitant medication;
 
4. Vital signs, physical examination;
 
5. Transplantation mode and preprocessing scheme;
 
6. Blood test: blood routine, blood biochemical (including liver and renal functions), virus infection;
 
7. Pregnancy tests (women of childbearing age);
 
8. Eligibility criteria review.
 
 
Visit 1(Day 15 after Allo-HSCT, Initial treatment)
 
 
1. Blood test: blood routine, blood biochemical (including liver and renal functions);
 
2. Vital signs, physical examination;
 
3. Concomitant medication, including PLT transfusion;
 
4. Adverse events.
 
 
Visit 2-9 (one visit per 1~2 weeks. Visit 2, day 21±2; visit 3, day 28±2; visit 4, day 35±2; visit 5, day 42±2; visit 6, day 49±2; visit 7, day 56±2; visit 8, day 62±2; visit 9, day 70±2 after Allo-HSCT)
 
 
1. Blood test: blood routine, blood biochemical (including liver and renal functions);
 
2. Vital signs, physical examination;
 
3. Concomitant medication, including PLT transfusion;
 
4. Adverse events;
 
 
(Participants who achieved PLT reconstruction during the core and extended study period directly enter the follow up period;
 
Participants who do not respond to the standard

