-----------------------	--------------------------------------------------------------------------------------------------------------------------------------------------------------------------------------------------------------------------------------------------------------------------------------------------------------------------------------------------------------------------------------------------------------------------------------------------------------------------------------------------------------------------------------------------------------------------------------------------------------------------------------------------------------------------------------------------------------------------------------------------------------------------------------------------------------------------------------------------------------------------------------------------------------------------------------------------------------------------------------------------------------------------------------------------------------------------------------------------------------------------------------------------------------------------------------------------------------------------------------------------------------------------------------------------------------------------------------------------------------------------------------------------------------------------------------------------------------------------------------------------------------------------------------------------------------------------------------------------------------

	
treatment can enter the extended study after visit 3 to receive avatrombopag treatment)
 
Visit 10 (day 28±5 after achieved PLT reconstruction)
 
 
1. Vital signs, physical examination;
 
2. Blood test: blood routine, blood biochemical (including liver and renal functions).
 
 
Long-term follow up is recommended.
 
Adverse events are closely observed and concomitant medication is recorded in detail during the study.

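### Repeated-measures ANOVA of platelet trends would drop mostly responders, and more of them from the better arm, because scheduled visits end at reconstruction

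*Combined protocol and SAP*

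**What the plan says.** - **Method.** Statistical analysis method: "PLT and other mean variation trends were processed by repeated measurement data analysis of variance". The section adds "The statistical process and graph were all run on SPSS 13.0 software" but names no procedure, no visits to be analysed and no rule for missing visits.
- **Schedule.** Study process sets Visits 2-9 at "one visit per 1~2 weeks", from day 21 to day 70 after transplant, each with a routine blood count. Treatment starts at Visit 1 (day 15). Visit 5 (day 42±2) falls at about the end of the four-week core study (15 + 28 = day 43).
- **Exit at reconstruction.** Study process: "Participants who achieved PLT reconstruction during the core and extended study period directly enter the follow up period".
- **What remains afterwards.** Treatment Design: "PLT count is measured for one time during the follow up". Study process places that visit at "Visit 10 (day 28±5 after achieved PLT reconstruction", a clock that starts at each patient's own reconstruction and so does not match the common visit days.
- **Outcomes.** Outcome Measure does not list mean platelet trend. It does list neutrophil and haemoglobin reconstruction as a secondary outcome. The primary outcome is a proportion.

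**The concern.** The schedule stops a patient's regular counts because that patient has met the primary outcome criterion. A method that needs every visit then discards that patient. Missingness is caused by response and is larger in the arm expected to respond more, so those left are selected on outcome, and differently by arm. The planned platelet-trend comparison would describe mainly patients who did not reconstruct. It would understate a real drug effect and lose much of its power. Neutrophil and haemoglobin trends may be exposed in the same way if they fall under the other mean trends in that sentence. That is an inference, since the plan does not say so.

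**Working it through.** **1. Check of the response rates.** Sample size estimation gives 35% and 60%, two-sided alpha 0.05, power 0.90 and 79 per group. With the unpooled two-proportion formula:

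(1.960 + 1.282)² × (0.35×0.65 + 0.60×0.40) / 0.25² = 10.51 × 0.4675 / 0.0625 = 78.6, which rounds up to 79. The plan's figure reproduces.

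The section gives both 78 and 190 participants in total. I use 78 (39 per arm). The percentages below do not depend on that choice.

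**2. Complete cases through Visit 5.** Let p be the response rate and f the share of responders who still have every count, because reconstruction is recognised only at the last visit analysed. Complete cases = N × [(1 − p) + p × f]. The documents do not give f, so a range is shown for N = 39.

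| f (assumed) | avatrombopag | rhTPO | responders among completers, avatrombopag / rhTPO |
|---|---|---|---|
| 0 | 15.6 | 25.4 | 0% / 0% |
| 10% | 17.9 | 26.7 | 13% / 5% |
| 25% | 21.5 | 28.8 | 27% / 12% |
| 50% | 27.3 | 32.2 | 43% / 21% |

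At f = 0 the loss is 60% of avatrombopag and 35% of rhTPO patients. At 79 per arm the f = 0 counts are 31.6 and 51.4; at 95 per arm they are 38.0 and 61.8. Other dropout is ignored.

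**3. Direction of the bias.** For illustration, assume mean counts of 50 in responders and 12 in non-responders (×10⁹/L). The full-sample arm difference is (0.60 − 0.35) × 38 = 9.5. Among completers it is 38 × (difference in responder share): 0 at f = 0, 3.0 at 10%, 5.9 at 25% and 8.2 at 50%. It is smaller than 9.5 in every row.

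**4. Simulation for size.** All growth inputs are assumed: baseline log count normal with mean ln 12 and SD 0.25; log-linear growth with slope SD 0.045 per day; measurement SD 0.15; mean slopes tuned to 60% and 35% reconstruction by day 42. Power is for a t-test on patient slopes with 39 per arm.

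| Counts used | completers, avatrombopag / rhTPO | day-42 ratio | power |
|---|---|---|---|
| All patients, all counts | 39 / 39 | about 2.2 | about 82% |
| Completers, exit on the exact day the 7-day run ends | 16 / 26 | about 1.4 | about 24% |
| Completers, exit recognised at the next scheduled visit | 20 / 29 | about 1.5 | about 35% |

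In the last row responders are about 23% of avatrombopag and 13% of rhTPO completers. With no responders left at all, power is about 23%.

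**5. Does a mixed model repair it?** A model with unstructured visit means, fitted by maximum likelihood to the incomplete data, gives a ratio of 1.93-2.16 against a true 2.24 under log-linear growth. If counts instead plateau at 40 ×10⁹/L (assumed), it gives about 1.9 against a true 1.69. It recovers most of the effect in the first case and overstates it in the second.

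**The case against.** **A reader might infer that the test compares non-responders only.** The documents do not support that. The plan fixes neither the visits nor a missing-data rule, so the deletion follows from the classical form of the method rather than from stated text. Even with deletion through Visit 5, a patient whose reconstruction is first recognised at Visit 5 has every count. A shorter window keeps more responders. Nor do responders leave the study; they move to follow-up with one further count. These points stand, and they are why the size is given as a range. They do not remove the bias, and an unstated window leaves the choice open until the data are seen.

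**Some non-responders are lost as well.** Withdrawal criteria remove avatrombopag patients whose counts stay low after two weeks of "treatment of avatrombopag in a maximum dose of 60" mg/d, and rhTPO non-responders in "treatment can enter the extended study after visit 3 to receive avatrombopag treatment". This adds missing or post-switch counts; it does not make the complete cases comparable.

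**A reader might infer that the main efficacy result is at risk.** It is not. The primary outcome is a proportion. In the Kaplan-Meier/log-rank analysis of recovery, reconstruction is the event, not missing data.

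**A reader might also infer that a mixed model settles the matter because exit follows the observed counts.** That is too strong. Exit also depends on transfusion-free status and on a 7-day run that weekly counts do not fully show. A plateau is plausible, since Treatment Design has both drugs reduced and stopped from 50 ×10⁹/L.

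**Conclusion.** The concern holds in this form: a complete-case repeated-measures ANOVA through Visit 5 would rest mostly on non-responders, lose more patients from the better arm, and be biased toward no difference. The completer counts rest on the plan's response rates and on when reconstruction is recognised. The ratios and power rest on assumed growth and variances, and should be read as an indication of size, not a prediction. No figure was worked out for neutrophils or haemoglobin. The point is moderate and should be corrected before analysis, but it does not touch the primary comparison.

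**What to change.** - Replace repeated-measures ANOVA with a likelihood-based mixed model for repeated measures on log counts at Visits 1-5, using every observed count from all FAS patients, with arm, visit, arm-by-visit and the Visit 1 value. State that patients who leave the schedule at reconstruction stay in the model with the counts they have.
- State that missing-at-random is an assumption, why it may fail (transfusion-free status, daily runs), and that the model can overstate the effect if counts plateau after reconstruction.
- Add a sensitivity analysis: one that uses any routine counts recorded on the common visit days after reconstruction together with the Visit 10 count, or one that assumes a plateau.
- Say whether neutrophil and haemoglobin trends are analysed by the same model.
- Reconcile two pairs of statements that decide which counts exist. Follow-up is timed from product withdrawal in Treatment Design but from reconstruction in Study process. The rhTPO switch comes after the core study in Treatment Design but after Visit 3 (day 28) in Study process. State how post-switch counts within Visits 1-5 are handled.

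The cost is SAP wording and one extra model fit. No patients are added, and the sensitivity analysis needs no new procedure if it uses counts already recorded. If the named software version does not fit the model, name another standard package.

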**Outcome Measure**

**Primary outcome measures**

- Percentage of participants whose PLT reaches ≥

	
20*10^9/L without the need for PLT transfusion for consecutive 7 days during core study
 
Secondary outcome measures
 
 
• Percentage of participants whose PLT reaches ≥ 20*10^9/L without the need for PLT transfusion for consecutive 7 days during extended study;
 
• Percentage of participants without PLT response in the standard group but with PLT reconstruction after receiving avatrombopag;
 
• Percentage of participants with PLT ≥ 50*10^9/L without the need of PLT transfusion for consecutive 7 days during the core and extended study;
 
• The time to achieve PLT ≥ 20*10^9/L without the need of PLT transfusion for consecutive 7 days in both group;
 
• Proportion of participants achieving platelet reconstitution after 4 weeks of drug withdrawal;
 
• Volume of PLT transfusion;
 
• Hematopoietic reconstruction condition (absolute neutrophils, hemoglobin)
 
 
PLT reconstruction is defined as the status of PLT ≥ 20*10^9/L without the need of PLT transfusion for consecutive 7 days.

pSafety Measure
	
 
1. Liver and renal functions;
 
2. Occurrence and severity of transplantation-related complications;
 
3. Bleeding risk (WHO bleeding assessment scale);
 
4. Adverse events.
 

Study
	
Screening stage (Day 10~14 after Allo-HSCT)

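### Kaplan-Meier is assigned to relapse, transplant-associated mortality, GVHD and platelet recovery with no rule for competing events, so these cumulative rates are overstated whenever competing events intervene

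*Combined protocol and SAP*

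**What the plan says.** Under Statistical analysis method, one sentence covers five quantities. It begins "Kaplan-Meier survival analysis was used to estimate the recovery of PLT count, cumulative predicted survival rate", continues with "cumulative recurrence rate of malignant hematologic disease, cumulative mortality associated with transplantation, and cumulative incidence of GVHD", and ends "and log-rank test was performed". A later sentence adds "OS and DFS are estimated by Kaplan-Meier method". DFS and transplant-associated mortality are not defined. The synopsis names no competing event, censoring rule, cumulative incidence estimator or Gray's test.

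Of these quantities, only platelet recovery is a listed efficacy outcome in time-to-event form. The secondary outcomes include the time to reach the count threshold "without the need of PLT transfusion for consecutive 7 days in both group". The same statistical section also assigns platelet recovery time to one-way analysis of variance. Relapse, transplant-associated mortality, OS and DFS are not listed outcome measures. GVHD fits at most under transplantation-related complications in the safety measures.

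Two further places matter:

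- Withdrawal criterion 1 removes patients whose count stays below 20 × 10⁹/L on avatrombopag, with the note "Solution: receive other treatment after withdrawal from the study".
- Under Study process, the treatment-period schedule ends at "visit 9, day 70±2 after Allo-HSCT". One visit follows about 28 days after reconstruction, and beyond that "Long-term follow up is recommended".

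**The concern.** Death without relapse rules out relapse. Death rules out later GVHD and later platelet recovery. If transplant-associated mortality means death without relapse, relapse rules it out. Kaplan-Meier handles such patients as censored, as though they could still have the event at the same rate as those who remain at risk. The complement of that curve is not the proportion of patients who have the event by a given time, which is what a cumulative rate or cumulative incidence is taken to mean.

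The reported rates could therefore be too high. The relapse and mortality figures might not reconcile with the plan's own DFS. The platelet-recovery curves could also be inflated by different amounts in the two arms. Withdrawal for non-response raises a separate problem for platelet recovery: patients who leave because their count stayed low are unlikely to recover at the same rate as those who stay, so censoring them at withdrawal is informative.

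**Working it through.** **Inputs.** From the documents: Kaplan-Meier and log-rank for all these curves, and platelet response of 35% (control) and 60% (avatrombopag) from the sample size paragraph. Those two rates describe the primary endpoint and are borrowed here only to size the bias. The documents give no rate for relapse, transplant-associated mortality, GVHD or death before recovery, so all of these are assumed over a range. There is no plan figure to reproduce.

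**Direction, with no assumed rates.** Let Λₖ be the cumulative cause-specific hazard of event k, KMₖ the Kaplan-Meier curve with competing events censored, and S the probability of being free of all the competing causes. Then

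- true cumulative incidence: CIFₖ(t) = ∫ S(u−) dΛₖ(u)
- one minus Kaplan-Meier: 1 − KMₖ(t) = ∫ KMₖ(u−) dΛₖ(u)

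S is never above KMₖ, so 1 − KMₖ is never below CIFₖ. It is above it once a competing event has occurred and events of type k follow.

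**Additivity for relapse and mortality.** Assume DFS is freedom from relapse or any death, and transplant-associated mortality is all non-relapse death. In continuous time KM₁ × KM₂ = DFS, so

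(1 − KM₁) + (1 − KM₂) − (1 − DFS) = (1 − KM₁)(1 − KM₂).

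**Size under constant hazards.** For true incidences a and b at the horizon, H = −ln(1 − a − b), and the estimate for the first event is 1 − exp(−H·a/(a + b)).

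Example with a = b = 0.20: H = −ln(0.60) = 0.5108, and 1 − exp(−0.2554) = 0.2254 for each event. The sum is 0.4508 against 0.40. The excess is 0.0508, which equals 0.2254².

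| Assumed relapse / mortality | 1 − KM for each | Sum | 1 − DFS | Excess (points) |
|---|---|---|---|---|
| 5% / 5% | 5.13% | 10.26% | 10% | 0.26 |
| 10% / 10% | 10.56% | 21.1% | 20% | 1.1 |
| 20% / 20% | 22.5% | 45.1% | 40% | 5.1 |

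A simulation of 400,000 patients at 20% / 20% gave a sum of 45.1% against 40.0% for the composite.

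Platelet recovery, with the same assumed competing incidence in both arms:

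| Competing event before recovery | True 35% becomes | True 60% becomes | Difference (true: 25 points) |
|---|---|---|---|
| 2% | 35.4% | 60.8% | 25.4 |
| 5% | 36.0% | 62.1% | 26.0 |
| 10% | 37.2% | 64.4% | 27.2 |
| 20% | 39.8% | 70.1% | 30.3 |

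For 60% with 10%: H = −ln(0.30) = 1.2040, share 0.6/0.7, and 1 − exp(−1.0320) = 0.6437. The bias is larger in the arm with more recovery, so the difference widens even when competing rates are equal.

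GVHD: 20% with 5% competing events becomes 20.6%, 30% with 10% becomes 31.8%, and 40% with 20% becomes 45.7%.

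**Withdrawal.** The documents give neither the number nor the timing of non-response withdrawals, so no size is attached to this part.

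**The case against.** The strongest reply has five parts.

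1. *The plan never says that competing events are censored.* This is true. Censoring is inferred from plain Kaplan-Meier with no other rule. The inference is fair, because that is what following the text produces, but the defect is a missing rule rather than a stated wrong one.

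2. *The rates may be low.* Entry requires expected survival above 3 months and excludes detected recurrence, steroid-resistant GVHD and severe uncontrollable infection. Scheduled treatment visits end near day 70. At 5% event rates the bias is 0.26 points in the relapse and mortality sum and 1 to 2 points in platelet recovery. This stands as a limit on size. The bias grows if the curves are carried into longer follow-up.

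3. *The DFS mismatch depends on definitions.* A reader might infer that all four curves fail to add up to DFS, or that the plan's figures must be mutually impossible. The documents do not support either reading. GVHD and platelet recovery are not components of DFS under any estimator. If some non-relapse deaths are not counted as transplant-associated, the relapse and mortality sum need not exceed 1 − DFS.

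4. *Log-rank is not invalid.* It remains a proper comparison of cause-specific hazards. It does not test the cumulative incidences that the plan names.

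5. *The effect of withdrawals may be small.* On one reading, criterion 1 needs two weeks at 60 mg/d, a dose that the avatrombopag arm reaches only in the extension. Such withdrawals would then come no earlier than about week 6 of 8 (4 + 2), leaving little time for later recoveries to inflate the curve. But the treatment design also makes entry to the extension conditional on not meeting the withdrawal indication, which implies that it can be met in the core stage. These passages must be reconciled. A claim of large inflation from withdrawals has no support in the documents.

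**Conclusion.** The point holds in a limited form. Four quantities with competing events are assigned an estimator that does not give their cumulative incidence, and no rule says otherwise. The direction of the error is certain once a competing event precedes later events of interest. Its size is not known, because every rate except the plan's 35% and 60% is assumed, and constant hazards are assumed throughout. On those assumptions it runs from negligible at low event rates to about 5 points in the relapse and mortality sum at 20% each. The excess over 1 − DFS rests on the two definitions stated above and concerns only relapse plus non-relapse mortality.

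A reader might infer that the trial's main conclusion is at risk. It is not on this account: the primary endpoint is a percentage during the core study and uses none of these curves. The effect is confined to one listed secondary endpoint, time to platelet recovery, and to the transplant-outcome curves. The point is of moderate weight.

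**What to change.** Amend the Statistical analysis method section before the data are analysed:

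- Keep Kaplan-Meier and log-rank for OS and DFS. Define DFS, and define which deaths count as transplant-associated.
- Use the Aalen-Johansen cumulative incidence function for the other four, naming the competing events: for relapse, death without relapse; for transplant-associated mortality, relapse and any other death not counted as transplant-associated; for GVHD, death without GVHD; for platelet recovery, death before recovery. Relapse does not preclude GVHD, so treating it as a competing event there is a choice to be stated.
- Compare cumulative incidences with Gray's test. If log-rank is kept, label it as a comparison of cause-specific hazards.
- For platelet recovery, do not treat withdrawal for non-response as non-informative censoring. State the estimand. One option is to count these patients as not recovered to the end of the window, with a sensitivity analysis. This is an estimand choice, since they go on to other treatment. State as well how rhTPO non-responders who move to avatrombopag in the extension enter the curve.
- Name one method for platelet recovery time, since the section now gives both Kaplan-Meier and one-way analysis of variance.

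The cost is SAP wording and a package with competing-risk routines alongside SPSS 13.0. No new data are needed beyond the event dates and causes of death that the planned curves already require.

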
Statistical Analysis
	
 
• The sponsor will utilize appropriately qualified individuals to supervise the conduct of the trial to make sure the data collection, entry and management are in accordance with good clinical practice (GCP);
 
• Corresponding database will be established and source data will be input independently;
 
• Data administrator uses Epidata software to compile data entry program and carry out following process. Two data administrators will independently enter and proofread the data in double copies to ensure the accuracy.
 
 
Sample size estimation
 
 
• 78 participants
 
 
Based on the known literature, 35% of patients in the control group and 60% of patient in the trial group were

estimated to achieve the primary endpoint. Under the condition of the number ratio of control to trial group 1:1,  $\alpha=0.05$  (bilateral) and  $1-\beta=0.9$ , the number of participants in the control group and the test group was 79 and 79 respectively, calculated by the pros and cons test method of the clinical controlled study with PASS software. Further taking into account a 20% shedding rate per group, 95 cases per group were actually needed, for a total of 190 cases

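### One blanket P ≤ 0.05 rule covers about ten named tests beyond the primary outcome, with no order, adjustment or exploratory label, so a false significant claim among them has a chance of up to about 40%

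*Combined protocol and SAP*

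**What the plan says.** The Outcome Measure section names one primary outcome: the percentage of participants reaching the platelet threshold, transfusion-free for seven days, during the core study. Sample size estimation is built on that outcome alone, with "35% of patients in the control group and 60% of patient in the trial group were" expected to reach it, at a two-sided 5% level and 90% power.

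The Statistical analysis method section sets one rule for everything: "All tests were bilateral, and $P \leq 0.05$ was considered to be significant". It assigns tests to these quantities:

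- Log-rank tests for platelet recovery, survival, recurrence of the malignant disease, transplant-associated mortality and GVHD. The sentence ends "cumulative mortality associated with transplantation, and cumulative incidence of GVHD, and log-rank test was performed".
- Repeated-measures analysis of variance for the platelet trend and an unstated number of other trends.
- A nonparametric test for cumulative platelet demand.
- One-way analysis of variance for platelet recovery time, granulocyte engraftment time and number of platelet infusions.

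OS and DFS are additionally to be estimated by Kaplan-Meier; that sentence names no test. No test is named for the primary percentage. The document gives no testing order and no adjustment, and does not label any analysis exploratory.

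**The concern.** A 5% threshold controls error for one test. Applied separately to a set of tests, it leaves the chance of a false finding somewhere in the set uncontrolled. Under the written rule, a trial that misses its primary outcome could still report a significant benefit on another endpoint and be following its plan.

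Two features make this more than a formality. Platelet recovery has both a log-rank test and an analysis of variance, and platelet transfusion has both a nonparametric test and an analysis of variance. Neither pair has a governing method, so the more favourable P value can be used. Survival and relapse appear nowhere in the Outcome Measure section, yet the rule treats a P value on them exactly as it treats one on the primary outcome.

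A missed primary outcome is also a realistic prospect. The synopsis gives 78 participants in one place and a calculated 190 in another. That conflict is a separate matter, but at 78 the power for the assumed difference is only about 60%.

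**Working it through.** **1. The plan's own figure.** Inputs from Sample size estimation: 35% and 60%, two-sided 0.05, power 0.90, 1:1 allocation. With the unpooled normal formula,

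n = [0.35×0.65 + 0.60×0.40] × (1.960 + 1.282)² / 0.25² = 0.4675 × 10.51 / 0.0625 ≈ 78.6, so 79 per group.

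This matches the statement that "the number of participants in the control group and the test group was 79 and 79 respectively". The whole 5% is spent on one comparison, with nothing set aside for others.

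**2. Count of the other named tests** (Statistical analysis method):

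- log-rank: 5
- repeated-measures: 1 at least, since the number of other trends is not given
- nonparametric: 1
- one-way analysis of variance: 3

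Total k = 5 + 1 + 1 + 3 = 10. This reads the log-rank clause as covering all five quantities in its sentence and the comparisons as between arms. Counting platelet recovery once and platelet transfusion once gives k = 10 − 2 = 8.

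**3. Chance of at least one false significant result,** every null hypothesis true and tests independent: 1 − 0.95^k.

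- k = 10: 1 − 0.5987 = 0.401
- k = 8: 1 − 0.6634 = 0.337

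**4. Allowing for dependence.** The documents give no correlations, so a common correlation is assumed. Simulating 200,000 sets of equicorrelated two-sided z tests, all nulls true, gives:

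| Assumed correlation | k = 10 | k = 8 |
|---|---|---|
| 0.3 | 35% | 30% |
| 0.5 | 29% | 25% |
| 0.7 | 21% | 19% |
| 0.9 | 13% | 12% |

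Even at 0.9 the figure is more than twice 5%.

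**5. Off-list check.** The Outcome Measure section covers platelet responses, time to platelet response, platelet transfusion volume, and neutrophil and haemoglobin recovery. Survival and relapse are absent. GVHD and transplant mortality are not listed by name, but the safety measures include transplantation-related complications, which may cover them.

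**6. Power at 78 participants** (39 per arm, pooled-variance normal formula): (0.25×√39 − 1.960×√(2×0.475×0.525)) / √0.4675 = (1.561 − 1.384) / 0.684 ≈ 0.259, which is power of about 60%.

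**The case against.** The strongest reply is that the plan already has a hierarchy. It separates one primary outcome from the secondary ones and sizes the trial on the primary. The rule is a nominal per-test threshold, and nowhere does the plan say that a significant secondary result makes the trial positive. On this view any harm comes from later reporting.

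Part of this stands. The primary test keeps its 5% error rate, and a reader who infers that the primary's type I error is inflated would be wrong. But the primary/secondary split does not limit the significance rule, which covers all tests, including those of outcomes that are neither primary nor secondary.

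The reply is also right about several stronger readings:

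- A reader might put the figure at 40% to 56%. The upper end needs 16 tests, for example by adding the six risk-factor screens (1 − 0.95^16 = 0.560). Those screens are not treatment comparisons and have their own P < 0.05 sentence. Adding the secondary percentages does not help either, because no test is named for them, and one concerns only standard-group non-responders who switch to avatrombopag.
- Nor is 40% a floor. The tests are plainly dependent: two outcomes are tested twice, and survival, relapse and transplant mortality overlap. For ten tests, 40% is close to a ceiling.
- A reader might count DFS among the tested outcomes. The plan only estimates it, so the significance rule does not reach it.
- A reader might call GVHD and transplant mortality off-list without qualification. The safety item makes that contestable.

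**Conclusion.** The concern holds in a limited form. The plan calls every test significant at two-sided P ≤ 0.05, and so permits significance claims on about ten comparisons besides the primary, at least two of them on outcomes it does not list. The chance of at least one false claim among these is up to about 40%, assuming independence and no true effect on any of them. It is 34% for eight distinct endpoints under the same assumptions, and about 13% to 35% for ten tests under assumed common correlations of 0.9 to 0.3. The correlation range is an assumption, and ten is the count of tests the text identifies; the unnumbered other trends would add to it. The weakness lies in what may be claimed from the remaining results, and the primary analysis itself is sound on this point. It should be corrected, and correcting it is cheap.

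**What to change.** Replace the blanket significance sentence in Statistical analysis method with wording to this effect: the core-study primary percentage is the only comparison on which significance is declared, at two-sided 0.05; all other between-arm comparisons are reported as estimates with 95% confidence intervals, any P values being nominal, are labelled exploratory, and carry no claim of significance.

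In the same section:

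- name one governing method for platelet recovery time and one for platelet transfusion;
- label survival and relapse as exploratory, and GVHD and transplant mortality as safety or exploratory;
- name the test for the primary percentage, since significance would otherwise be reserved for a test the section does not specify;
- edit the log-rank, nonparametric, analysis-of-variance and risk-factor sentences to agree.

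The confirmatory error rate is then 5%. No extra participants, visits or data are needed. The cost is that secondary results cannot be called significant, and several sentences change rather than one. If the sponsor wants a formal claim on a secondary outcome, a prespecified fixed sequence after the primary would also hold the error at 5%. Bonferroni over the ten tests would require 0.05/10 = 0.005 for each.
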